12.5 Primary Analysis

12.5.1 Primary Endpoint Analysis Variables

The primary endpoints are:

- COHb on Day 5

Data and information contained in this document are considered to constitute trade secrets and confidential commercial information, and the legal protections provided to such trade secrets and confidential information are hereby claimed under the provisions of applicable law. No part of this document may be publicly disclosed without the written consent of Philip Morris Products S.A.

- MHBMA on Day 5
- 3-HPMA on Day 5
- S-PMA on Day 5
- Total NNAL on Day 90.

See Section 3.4.1.

Evaluation criterion:

The study will be considered successful, if the study demonstrates a 50% reduction or more for all five primary BoExps in the THS 2.2 Menthol arm compared to the CC arm, using a one-sided test test with 2.5% type I error probability.

12.5.2 Baseline Comparability

Not applicable.

12.5.3 Descriptive Analysis

Primary endpoints will be summarized as described in Section 12.1.3 on the PP.

12.5.4 Confirmatory Analysis

The hypothesis to be tested is that the geometric mean level of the BoExp for THS 2.2 Menthol is lower relative to mCC.

For primary BoExp, the hypothesis will be tested on Day 5 for monohydroxybutenyl-mercapturic acid (MHBMA), 3-hydroxypropylmercapturic acid (3-HPMA), S-phenylmercapturic acid (S-PMA), and carboxyhemoglobin (COHb), and on Day 90 Visit for total 4-(methylnitrosamino)-1-(3-pyridyl)-1-butanol (total NNAL) according to the primary and secondary objectives.

Analysis of BoExp will be conducted on the natural log scale. In order to test the follow hypothesis:

Null hypothesis (H0): $m1 \geq m2$

Alternative hypothesis (H1): $m1 < m2$

Where m_1 and m_2 are the geometric means of the biomarker levels on Day 5 or on Day 90 for THS 2.2 Menthol and mCC respectively.

The transformed BoExp data will be analyzed by means of a generalized linear model using product arm as covariate adjusting for the following baseline information: sex, average cigarette consumption over the previous 4 weeks, and baseline value of endpoint. The test will be declared significant if the contrast THS 2.2 Menthol vs mCC is significant. Estimates of differences between groups will be back-transformed to provide relative effects.

Assumptions of the ANOVA model will be tested. Markedly non-lognormally distributed BoExp data will be transformed or analyzed by appropriate non-parametric methods.

Should more than 20% of the subjects be excluded from the PP, would the above confirmatory analysis be repeated on the Compliant Population.

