5.5.2 Evaluation Criteria

The study will be considered successful if the study demonstrates a 50% reduction or more in MHBMA, 3-HPMA, S-PMA, and COHb on Day 5, and in Total NNAL at the Day 90 Visit in smokers switching from mCC to THS 2.2 Menthol as compared to smokers continuing to smoke mCC, using a one-sided test with 2.5% type I error probability.

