12.6.1 Primary Analyses

12.6.1.1 Analysis of Biomarkers of Exposure for Primary Objectives

The BoExp (COHb in blood and urinary concentrations of MHBMA, 3-HPMA, S-PMA and Total NNAL) used for the primary analysis will be described as detailed in Section 12.1.3 “Descriptive Statistics”. The listing of the COHb data will have a flag for whether a subject’s COHb was <2%.

The baseline is as defined in Section 12.1.4 “Definitions for Statistical Data Analysis”.

The primary endpoints will be log-transformed (base_e) prior to analysis. The analysis will compare the evening COHb level (20:00-21:30) at Day 5; and urinary concentrations of MHBMA, 3-HPMA and S-PMA adjusted for creatinine on Day 5 and urinary concentrations of Total NNAL adjusted for creatinine on Day 90 Visit between the THS 2.2 Menthol and mCC arms for the PP Set. An analysis of covariance (ANCOVA) (Snedecor and Cochran 1982) model will be used with terms for the log-transformed baseline value, sex, average daily mCC consumption over the last 4 weeks as reported during screening and randomization arm.

The SAS code to be used for the THS 2.2 Menthol and mCC data is shown below:

```
Proc glm data=_data_ ;
  Class randomization_arm sex cigarette_cons;
  Model log_biomarker = log_baseline sex cigarette_cons
    randomization_arm;
  Lsmean randomization_arm / pdiff =control('mCC') alpha=0.05 cl;
  Run;
```

The least squares (LS) means and estimate of the difference and the 95% CI will be back-transformed. The geometric LS means for each randomization arm along with the ratio (THS 2.2 Menthol : mCC), two-sided 95% CI and one-sided p-value will be presented in the tables. THS 2.2 Menthol : CC effects will be graphed in a forest plot.

All figures, summaries and analyses will be performed on the PP Set. Additional descriptive statistics will be provided within the secondary analysis.

The data will be presented in the below outputs:

TFL number	Title
FIGURES	
15.1.1.1	Forest Plots of Statistical Analysis of Biomarkers of Exposure for Primary Objective – PP Set
15.1.1.2	Biomarker of Exposure for Primary Objective Arithmetic Mean and 95% CI for Percent Change from Baseline – PP Set
TABLES	
15.2.3.1.1	Analysis of COHb, MHBMA, 3-HPMA, S-PMA and Total NNAL on Day 5/90 Visit for THS 2.2 Menthol versus mCC for the Primary Objective – PP Set
15.2.4.1.1	Descriptive Statistics of Blood COHb (%) – PP Set
15.2.4.1.1.1	Descriptive Statistics of Blood COHb (%) by Sex – PP Set

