12.6.1.2 Confirmatory Analysis

The hypothesis to be tested is that the geometric mean level of the BoExp for THS 2.2 Menthol is lower relative to mCC and will be as described in Section 12.6.1.1 "Analysis of Biomarkers of Exposure for Primary Objectives".

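### The confirmatory test is written against any reduction (null ratio 1), while study success requires a demonstrated reduction of at least 50% (null ratio 0.50)

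*Protocol*

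**What the plan says.** **Success criterion.** Protocol 12.5.1 states: "The study will be considered successful, if the study demonstrates a 50% reduction or more for all five primary BoExps", with a one-sided test at 2.5%. Protocol 3.4.1 and the synopsis say the same. SAP 5.5.2 repeats it ("The study will be considered successful if the study demonstrates a 50% reduction or more in MHBMA, 3-HPMA, S-PMA, and COHb on Day 5") and adds Total NNAL at the Day 90 Visit.

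**Confirmatory test.** Protocol 12.5.4 sets the null that the geometric mean under THS 2.2 Menthol (m1) is at least that under mCC (m2), against the alternative that it is lower. The rule is "The test will be declared significant if the contrast THS 2.2 Menthol vs mCC is significant". SAP 12.6.1.2 reads "The hypothesis to be tested is that the geometric mean level of the BoExp for THS 2.2 Menthol is lower relative to mCC" and refers to 12.6.1.1 for the method. There the code fits an ANCOVA to the log biomarker and compares the arm LS means with mCC as control, which tests a log difference of zero. The reported output is the back-transformed ratio, for which a "two-sided 95% CI and one-sided p-value will be presented in the tables".

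**Multiplicity.** Protocol 12.1.5 and SAP 12.1.7 require statistical significance on all primary endpoints before any confirmatory claim. SAP section 9, which lists the changes from the protocol, does not mention the null value.

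**The concern.** As a hypothesis test, the success criterion has the null m1/m2 ≥ 0.50. The test written down has the null m1/m2 ≥ 1. These are different questions, and the p-value planned for the tables answers only the second. It limits to 2.5% the chance of a significant result when there is no reduction at all. It says nothing about error when the true reduction is real but below 50%, which is the error that matters for the claim the trial is meant to support.

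Because the plan does not say how the criterion is to be judged, three readings are open:

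- p below 0.025 against ratio 1;
- that p-value together with a point estimate below 0.50;
- an upper confidence limit below 0.50.

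Only the third delivers the stated 2.5%. Under the second, an endpoint whose true ratio is exactly 0.50 passes about half the time, since the log-scale estimate is symmetric about ln 0.5.

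**Working it through.** **Inputs** (Protocol 12.2, Tables 19 to 22; SAP section 8). Mean ratio (CV):

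| Endpoint | YVD-CS01-EU | ZRHX-EX-01 | n (THS:mCC) |
|---|---|---|---|
| COHb | 0.40 (0.32) | 0.44 (0.14) | 80:40 |
| 3-HPMA | 0.30 (0.50) | 0.28 (0.20) | 80:40 |
| MHBMA | 0.15 (0.70) | 0.11 (0.47) | 80:40 |
| S-PMA | 0.20 (0.70) | 0.07 (0.50) | 80:40 |
| Total NNAL | 0.30 (0.60) | 0.30 (0.60) | 40:40 |

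The Total NNAL figures come from a separate 12-week study and serve both scenarios.

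**Method.** Log-scale SD σ = √ln(1 + CV²); SE = σ√(1/n1 + 1/n2); power from the noncentral t with noncentrality ln(margin/true ratio)/SE, one-sided 2.5%. Joint power is the product over the five endpoints. Independence is an assumption; the documents give no correlations.

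**Step 1: reproduce the plan's power with margin 0.50.**

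- COHb, YVD: σ = 0.312, SE = 0.0605, ln(0.50/0.40) = 0.223, power 0.9555.
- COHb, ZRHX: σ = 0.139, SE = 0.0270, ln(0.50/0.44) = 0.128, power 0.9969.
- Total NNAL: σ = 0.555, SE = 0.124, ln(0.50/0.30) = 0.511, power 0.9825.
- The other three: 0.9998 or more in both scenarios.
- Joint: 0.9386 (YVD) and 0.9795 (ZRHX). Table 23 states 94% and 98%.

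**Step 2: the same calculation with the null as written (margin 1).** Joint power exceeds 99.99% in both scenarios. The stated power therefore belongs to a test at 0.50, not to the test in 12.5.4.

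**Step 3: observed reduction needed to pass.** Against ratio 1 it is 1 − exp(−t·SE); against 0.50 it is 1 − 0.5·exp(−t·SE), with t the 97.5% point.

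| Endpoint | Ratio 1: YVD / ZRHX | Ratio 0.50: YVD / ZRHX |
|---|---|---|
| COHb | 11% / 5% | 56% / 53% |
| 3-HPMA | 17% / 7% | 58% / 54% |
| MHBMA | 21% / 16% | 61% / 58% |
| S-PMA | 21% / 17% | 61% / 58% |
| Total NNAL | 22% / 22% | 61% / 61% |

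**Step 4: probability that all five tests are significant when the criterion is not met.** Endpoints not named keep their planned ratios.

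| True state | Null ratio 1: YVD / ZRHX | Null ratio 0.50 |
|---|---|---|
| COHb ratio 0.50 | 1.00 / 1.00 | 0.025 |
| COHb ratio 0.80 | 0.96 / 1.00 | effectively 0 |
| Total NNAL ratio 0.70 | 0.81 / 0.81 | about 2 in a million |
| All five at 0.60 | 0.95 / 0.98 | effectively 0 |
| All five at 0.70 | 0.54 / 0.77 | effectively 0 |

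The null-ratio-1 column gives probabilities of significance against ratio 1. They are probabilities of false success only if the written test is taken as the success rule.

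**The case against.** The strongest reply is that the plan has two layers: a hypothesis of any reduction (SAP 5.5.1) and a stricter success criterion with its own alpha (SAP 5.5.2). No passage says that p below 0.025 against ratio 1 makes the study a success. The planned two-sided 95% CI already holds the answer, because an upper limit below 0.50 is exactly the one-sided 2.5% test of the criterion. The probabilities in step 4 are correct rejections of the null as written, since exposure truly is lower in those cases. Even under the point-estimate reading, the risk away from the boundary is small: about 0.3% for Total NNAL at a true ratio of 0.70, and far less for COHb at 0.80.

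Much of this stands. The information needed will be in the tables, the model and estimates are sound, and a careful reader could apply the right rule. What does not stand is that the rule is specified. The criterion calls for a one-sided test, the only test written out uses another null, and the multiplicity sections tie confirmatory claims to significance on that test. The upper-limit rule appears nowhere.

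One further limit: only the 50% column of Table 23 reproduces closely. Some others do not (ZRHX at 53%: stated 76%, computed 64%; YVD at 55%: stated 38%, computed 44%), perhaps because of unrounded inputs. The 50% target is in any case plain from the text of Protocol 12.2.

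**Conclusion.** The concern holds: the confirmatory test is wrong as written for the claim it has to support. The sample size was set for a test at ratio 0.50, and the documents specify a test at ratio 1. This is a specification error and not a sample-size error. Its size is the gap between an observed reduction of about 5% to 22%, enough for significance as written, and about 53% to 61%, needed to demonstrate a 50% reduction. The planned p-value cannot establish success. The single-endpoint thresholds depend on the plan's CVs and analysed numbers; the joint probabilities also assume independent endpoints. The mismatch itself depends on none of these. It should be corrected before database lock, because it governs the trial's main conclusion.

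**What to change.** In SAP 5.5.1, 12.6.1.1 and 12.6.1.2, and in Protocol 12.5.4 if that is amended:

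1. State for each primary endpoint H0: m1/m2 ≥ 0.50 against H1: m1/m2 < 0.50.
2. Declare success only if the upper limit of the two-sided 95% CI for the back-transformed THS 2.2 Menthol:mCC ratio is below 0.50 for all five endpoints.
3. Compute the one-sided p-value from t = (LS-mean difference on the log scale − ln 0.5)/SE, lower tail.
4. Keep the null ratio of 1 for the secondary biomarkers, and say so explicitly, because Protocol 12.6.4 takes its hypothesis from 12.5.4 by reference.

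The cost is a few sentences and a short addition to the code. Joint power stays at the stated 94% and 98%, so the sample size and data collection are unaffected. A protocol amendment has to go to the IRB (Protocol 1.1). SAP v2.0 (07 Nov 2014) already postdates the expected study end (31 August 2014), so a SAP amendment before database lock, listed in section 9 as a change from the protocol, is the practical route.

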12.6 Secondary Analysis

12.6.1 Secondary Endpoint Analysis Variables

See Section 3.4.2.

More details on derivation rules will be given in the SAP.

12.6.2 Baseline Comparability

Not applicable.

12.6.3 Descriptive Analysis

In general, secondary endpoints will be summarized as described in Section 12.1.3 according to the populations as described in Section 12.4.

12.6.4 Inferential Analysis

For the secondary BoExp and selected risk markers, the hypothesis to be tested is the same as described in Section 12.5.4. This will be tested for secondary BoExp on Day 5, and if significant, on Day 90 (except Total NNAL).

12.6.5 Safety Analysis

In general, all safety data will be listed and tabulated on the safety population by product arm, using the approach described in Section 12.1.3. Safety variables collected during exposure periods will also be reported by product exposure.

Adverse events data will serve as the primary assessment of safety. Other safety variables monitored in this study include: respiratory symptoms (cough assessment VAS and Likert scales); vital signs (systolic and diastolic blood pressure, pulse rate, respiratory rate); spirometry; electrocardiogram (ECG) data; clinical chemistry, hematology, concomitant medications, and urine analysis safety panel; physical examination.

The number and percentage of subjects with AEs and SAEs will be tabulated by system organ class (SOC) and preferred term (PT), summarized for the safety population and the full safety population. Summaries will also be presented for AEs leading to withdrawal, AEs leading to Death, AEs by relatedness to product exposure, AEs by severity, and laboratory AEs. Tabulations will be performed for both the number of subjects experiencing an event and the number of events.

The number and percentage of subjects with clinical findings by sequence for laboratory parameters will be summarized for the safety population and the full safety population. Shift tables showing change from baseline of clinical findings will be provided for: ECGs, physical examinations and laboratory parameters (both shifts in normal ranges and toxicity grades). Descriptive statistics will be summarized by visit and change from baseline for laboratory parameters, ECG, respiratory symptoms, and vital signs.

12.7 Exploratory Analysis

12.7.1 Exploratory Endpoint Analysis Variables

See Section 3.4.3.

12.7.2 Descriptive Analysis

In general, exploratory endpoints will be summarized as described in Section 12.1.3 according to the populations as described in Section 12.4.

12.7.3 Preference Analysis

At admission, subjects will be asked for their preferred product (THS 2.2 Menthol, mCC, no preference). A sensitivity analysis will be run for the exposure according to the subjects' preferred product.

Data and information contained in this document are considered to constitute trade secrets and confidential commercial information, and the legal protections provided to such trade secrets and confidential information are hereby claimed under the provisions of applicable law. No part of this document may be publicly disclosed without the written consent of Philip Morris Products S.A.

12.8 Demographics and Baseline Characteristics

Demographic and other baseline characteristics will be reported according to the populations as described in Section 12.4. Summary statistics will be provided by exposure group and stratified by sex and by cigarette consumption. Formal statistical analysis will not be performed on baseline demographic data.

12.9 Interim Analysis

There are no planned interim analyses.

13.2 Subject Confidentiality

All information obtained during the conduct of the study with respect to the subjects' state of health will be regarded as confidential. A statement to this effect will be written in the information provided to the subject. An agreement to disclose any such information will be obtained from the subject in writing and signed by the subject, in compliance with all local and national data protection and privacy legislation.

Data and information contained in this document are considered to constitute trade secrets and confidential commercial information, and the legal protections provided to such trade secrets and confidential information are hereby claimed under the provisions of applicable law. No part of this document may be publicly disclosed without the written consent of Philip Morris Products S.A.

The anonymity of subjects participating in this study will be maintained. Subjects will be identifiable by the Sponsor (or Sponsor's authorized representative) on eCRFs and other documents by their subject (or randomization) number/code, sex and date of birth, but **not** by name, initial, or any other details relating to identifiable person (e.g. address, health insurance ID card, medical chart number, etc.). The assignment of a subject number/code for subject identification will be based on the appropriate data protection rules.

Any documents that allow full identification of the subject (e.g. the subject's signed ICF) must be maintained in confidence by the Investigator. If any document relating to this study shows a subject's name or any other details relating to an identifiable person (e.g. address, health insurance ID card, medical chart number, etc), the name or other identifiable details must be obscured before a copy of that document is supplied to the Sponsor or the Sponsor's authorized representative.

13.3 Access to Source Documentation

Subjects will be informed that, during the course of the clinical study, the Sponsor, any authorized representatives of the Sponsor, IRB, or regulatory authorities may inspect their medical records to verify the information collected, and ensure that all personal information made available for inspection is handled in the strictest confidence and in accordance with national and local data protection and privacy legislation.

The Investigator/head of the investigational site and all study site collaborator involved with the study must permit direct access to source data/documents for study related monitoring, audits, IRB review, and regulatory inspection(s).

13.4 Record Retention

All records of data, source data and source documents (original records or certified copies), in any form (including, but not limited to, written, electronic, magnetic, optical records and scans, X-rays, and ECGs) that describe or record the methods, conduct, and/or results of the study, the factors affecting the study, and the actions taken will be maintained by the Principal Investigator/head of investigational site for the study, as required by ICH GCP and any other applicable local or national regulations. For X-rays at least the radiologist's assessment is required as source documentation. If the actual image is available it can be stored on CD as well.

Essential study documents/records, which individually and collectively permit evaluation of the conduct of a study and the quality of the data produced, are described in Article 41 of Ministerial Ordinance on GCP (Ministry of Health and Welfare, 1997). Essential documents

must be retained by the Principal Investigator or the head of the investigational site for a minimum of:

- At least 15 years after completion or discontinuation of the study, or
- At least 2 years depending on, for example, the circumstances, or
- After formal discontinuation of clinical development of the IP.

These documents should be retained for a longer period, however, if required by the applicable regulatory requirements or by an agreement with the Sponsor.

Examples of essential records/documents include, but are not limited to:

- Signed informed consent documents for all subjects and Master ICF.
- Subject identification code list, Screening Log and Enrolment Log (if applicable).
- Record of all communications between the Principal Investigator and the IRB, composition of the IRB.
- Record of all communications/contact between the Investigator, Sponsor, and its authorized representatives.
- List of sub-Investigators and other appropriately qualified persons to whom the head of the investigational site has delegated significant study-related duties, together with their roles in the study.
- Investigator Logs.
- eCRFs, study specific questionnaires (and associated data/scoring), subject diaries.
- Adverse event reports and details of follow-up investigations, details of concomitant medication.
- All other source documents (e.g. chest X-rays, ECGs, consultation reports, physical examination, laboratory records) or any electronically captured study source data.
- Clinical laboratory reports, laboratory normal ranges.
- Original medical/hospital records, if applicable (the medical files of study subjects must be retained in accordance with local legislation and in accordance with the maximum period of time permitted by the hospital or study site).
- Record of any body fluids or tissue samples collected and retained.
- Device Issue Log, IP Accountability Logs, dispensing records.
- Information regarding subjects' discontinuation and any follow-up.

Data and information contained in this document are considered to constitute trade secrets and confidential commercial information, and the legal protections provided to such trade secrets and confidential information are hereby claimed under the provisions of applicable law. No part of this document may be publicly disclosed without the written consent of Philip Morris Products S.A.

It is the responsibility of the Sponsor to inform the Principal Investigator/head of investigational site as to when these documents no longer need to be retained.

The Principal Investigator/head of investigational site must take measures to prevent accidental or premature destruction of these documents.

If the head of the investigational site wishes to assign the study records to another party or move them to another location, the Sponsor must be notified in advance.

The head of the investigational site must obtain written approval from the Sponsor before destruction of any records. Normally, these records will be held in the Investigator's archives. If the head of the investigational site is unable to meet this obligation, they must ask the Sponsor for permission to make alternative arrangements. Details of these arrangements must be documented.

The Sponsor or Sponsor's authorized representative will maintain documentation relating to the study as long as the IP is on the market, and/or for 15 years after the CSR has been finalized.

